Brief Title: Training Grammar With Meaning

Unique Protocol ID: DLD-Tx2

ClinicalTrials.gov Identifier: NCT06250101

September 8, 2025

1) Study Population

Participants will be between the ages of 4 and 6 years old and have a language impairment. Children will include both boys and girls. Given that boys are more often affected by this condition, we expect a slight excess of boys in the sample (e.g. 2:1 m:f). Subjects will be recruited from Tucson area preschools, kindergartens, daycare centers, and treatment programs. We intend to sample from geographic regions that are likely to produce a diversity of racial and ethnic backgrounds.

We anticipate that up to 300 children will participate over 6 years. Children will reflect all socio-economic levels (as indexed by mother's/guardian's educational level) with racial and ethnic distribution roughly equivalent to that of the Tucson population of children.

Power analyses indicate that between 16 and 24 children are required per study to find significant effects. Sample sizes may be adjusted to reflect actual effects as studies proceed. To get these numbers, we typically need to test 50 participants a year, with children not meeting the criteria for language impairment, children having insufficient numbers of potential treatment targets (speech/language errors) withdrawn after testing.

Inclusion criteria include:

Between ages 4 years 0 months and 6 years 11 months at the time of treatment onset.

Native English language development, with exposure to other languages acceptable.
Normal hearing as indicated by a pure-tone audiometric screening.

Normal nonverbal skills as indicated by the nonverbal scales of the Kaufman Assessment Battery for Children.

Impaired language as indicated by the Structured Photographic Language Test (monolingual English speakers) or the BESA (English/Spanish bilinguals).

Exclusion criteria include

Other handicapping conditions that could cause poor language skills (e.g., autism, intellectual disability, blindness, genetic disorders, neurologic disease or injury), by parent report.

Native language skills other than English.

Lack of functional English proficiency by *both* parents or *any* guardian.

2) Recruitment Methods and Consenting Process

a. Recruitment Process:

- 1) Recruitment flyers will be provided through preschools and daycares that include children with language impairments. The flyer is attached.
- 2) Parents can contact us directly (e.g., word of mouth referral, response to flyers, finding information on their own [e.g., past UA News items]). This item (UA News Items) covered only the preschool summer camp program as a community engagement piece. It is not used by us for recruitment, but parents do find it on the UA website.
- 3) Parents of children on waiting lists from previous years will be phoned to invite their child to enroll in the current year (if still age-eligible).

Parents contacting us through any means will be screened via telephone so that we can determine the likelihood of their child qualifying for the study.

b. Informed Consent:

A consent form will be used to obtain Parental Permission. Parents will be provided the consent form to read, and the points covered in the written document will be reviewed orally with the parents by the project staff (see VOTF). Parents will have the opportunity to ask questions at any time before or after providing consent. Parents will be provided both written and oral notification of major changes to the project (e.g., the nature of the treatment procedures used; project location) and oral notifications of minor changes (e.g., changes in start date, holidays).

Assent will be waived due to the ages of the children, as children are under the age of 7. We are asking for one parental signature. Please see Appendix A.

The consenting parent must have functional English skills for their child to participate [diagnosis of the disorder presumes adequate English exposure]. Therefore, no translators or translated documents will be used.

Consent and HIPAA documents are appended.

3) Research procedures involved in the Human Research

Total participation will last no more than 14 months. Participant qualification testing will occur over 1-4 days (depending on the child's ability to cooperate) up to 10 months prior to treatment.

Treatment will occur over a 6-week period with daily participation. Treatment-related procedures will last up to one hour per day. In addition to the treatment itself, children's language will be sampled periodically to determine which aspects of speech and language are in error and should be treated, as well as to track progress. Testing of verbal and nonverbal characteristics are obtained during the treatment period for 15 additional minutes approximately twice a week. To facilitate participation of low SES children [whose parents cannot miss work for their child's treatment], all children will be offered supervised day care, provided separately from the treatment, for up to 5 hours per day. Parents are

asked to return with their children between 2 and 4 months post treatment to measure retention of treatment effects.

This study will compare two variants of the same treatment. In one, children will be told the meaning of verbs that they will be prompted to use along with their grammatical target. In the other, children will not receive information on word meanings.

Treatment sessions will be audio and video recorded. This will apply to all children as a condition of participation. The recordings are needed to assess accuracy of treatment delivery and accuracy of the coding of children's responses to the treatment. We will request permission to use video recordings for training future students and clinicians. Consent will be indicated by the parent's initials on a line giving this consent on the PHI consent form. This consent is not required for the child to participate.

Participant qualification testing includes:

A pure-tone audiometric screening.

The nonverbal scales of the Kaufman Assessment Battery for Children. materials appended

The Structured Photographic Language Test (monolingual English speakers) or the BESA (English/Spanish bilinguals). materials appended

Treatment methods:

Treatment methods occur in an adult-child context in which the two are engaged in child-appropriate activities (e.g., board games, structured play, book reading, craft projects) and conversation. This treatment is known as Conversational Recast which is known to have an overall positive impact on children's language skills, based on published research by our group and others (going back into the early 1980s) Clinicians elicit language from the child by prompting them to use particular words, phrases, or sentences. After a child's response to the clinician's prompt, the clinician provides a correct model of the child's attempted utterance. Children are provided with at least 24 opportunities per session to attempt a treatment target and to receive feedback in the form of a correct repetition of the utterance or praise. No negative feedback is used.

It is not possible in advance to provide the exact words, phrases, or sentences used in treatment for multiple reasons. First, the linguistic units targeted for treatment are tailored to the errors of omission or commission for each individual child enrolled. These are never uniform across all children. Second, research considerations such as balancing particular targets across treatment groups influence the decision on what to treat, and therefore, the words used. Third, the treatment is not scripted and should not be scripted (scripted treatments have yielded poor effects in the previous literature). Fourth, our previous research has found that clinicians must use a large variety of words and contexts to train language for it to generalize to new linguistic and environmental contexts. It is not unusual for clinicians to use 75 different activities and well over 200 different

target words over the course of a treatment period. Finally, since treatment occurs in a conversational context with the child, treatment doses (the words spoken to children thought to effect change) often follow from what the child says, which is not predictable in advance.

Sessions are video and audio recorded so that the accuracy of treatment administration and coding of child utterances can be checked. These are used so that paper records can be checked for accuracy against a recorded record. Entire sessions are never transcribed, although individual words may be when it is important to record the exact sounds used in a child's production (e.g., him vs. he; bringed vs. brought, wabbit vs. rabbit).

Analysis plan

In this study, the dependent variable is expressed as change from baseline performance in units of standard deviation. This was designed to address the question of whether the treatment produced positive change overall. For this, we consider performance on the generalization probes from the first three pretreatment and final three end-treatment probe sessions. We calculate a single-subject effect size d metric that reflects gains in morpheme use from baseline levels, for each individual child. This is calculated for each of the Target and Control morphemes as follows:

$$\text{Generalization } d = \frac{(\text{end treatment probe mean} - \text{pretreatment probe mean})}{\text{end treatment standard deviation}}$$

We note that when the end treatment standard deviation was zero, we used the minimum possible standard deviation to avoid dividing by zero. We will compare the effect sizes of Target morpheme use to Control morpheme use for each group to determine the effects of treatment in terms of generalization to untreated words.

We used a Bayesian statistical approach to data analysis, using JASP software (JASP Team, 2021). For all tests, we will use the Bayesian equivalent of a Mann-Whitney U test for between group comparisons and a Wilcoxon signed-rank test for within-subject comparisons. Bayesian statistics do not require data to meet the assumptions of other parametric tests (e.g., t-tests), which the types of small samples used in early efficacy studies are unlikely to meet. Another important difference is that Bayesian statistics do not test for statistical significance but express the probability that two distributions are different. This probability is expressed as a Bayes Factor (BF), which can range from 0 to infinity, signaling that probability of a difference is highly unlikely to near certainty. A Bayesian approach can also evaluate the probability that two distributions are equivalent ($1/[BF]$ for group differences), which is not possible for traditional parametric statistics. For tests of within- or between-group differences, this expresses the range of effect sizes from within which the true effect is likely to fall. For correlations (Kendall's tau here), it expresses the range of correlations from which the true correlation is likely to fall.

As BFs increase above 1.0, support for the experimental hypothesis (e.g., group or condition differences) also increases. Guidance on the strength of support was provided by van Doorn et al., (2021), who suggested that BFs between 1 and 3 can be interpreted as providing

weak or incremental support for a hypothesis, moderate support indicated by BFs between 3 and 10, and strong support for BFs above 10. Although these values were suggested in the context of experimental research. We note, however, that comparison of two treatment methods that are each known to be efficacious, as will be the case here, is unlikely to result in a BF large enough to meet this criterion for “strong support”.

To address the effectiveness of the treatment, we will compare the treatment d for treated and control grammatical forms, collapsed across treatment conditions. To address whether providing semantic support improves learning, we will compare the treatment d for children who did and did not receive semantic support during treatment. To address the degree to which children retained learning after treatment concluded, we correlated (Bayesian Kendall’s Tau) the mean performance on the average of the final 3 generalization probes with performance at follow-up.

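### The retention analysis cannot show how much of the treatment effect persists: it is a rank correlation with no Target-versus-Control contrast at follow-up

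*Combined protocol and SAP*

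**What the plan says.** **Purpose of the visit.** Section 3, Research procedures, has parents "asked to return with their children between 2 and 4 months post treatment to measure retention of treatment effects". The same section gives the length of treatment: "Treatment will occur over a 6-week period with daily participation".

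**How a treatment effect is isolated at end of treatment.** The Analysis plan builds the effect size d from "performance on the generalization probes from the first three pretreatment and final three end-treatment probe sessions". Of d it says: "This is calculated for each of the Target and Control morphemes as follows". For effectiveness, "we will compare the treatment d for treated and control grammatical forms, collapsed across treatment conditions".

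**How retention is analysed.** The last paragraph of the Analysis plan states the question: "To address the degree to which children retained learning after treatment concluded". The answer is a Bayesian Kendall's tau correlating "the mean performance on the average of the final 3 generalization probes with performance at follow-up". The sentence names neither Target nor Control. No contrast between forms, no term for time since treatment and no record of services received in the interval is described.

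**Who the children are.** Section 1: "Subjects will be recruited from Tucson area preschools, kindergartens, daycare centers, and treatment programs". They are aged 4 to 6, and none of the listed criteria limits language therapy outside the study.

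**The concern.** The visit is meant to measure persistence of a treatment effect. The plan defines that effect as improvement on a treated form over and above improvement on an untreated one. At follow-up the untreated reference is not mentioned, and the statistic changes from a comparison of amounts to a correlation of ranks.

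Two faults follow. First, tau does not respond to the quantity asked about: it can be high when every child has lost most of the gain. Second, replacing tau with a comparison of Target scores at the two times would not be enough. Young children continue to acquire grammar, attend school and may receive therapy, so a steady Target score at follow-up could mean retention, or loss offset by growth. If a Control form is needed to rule out development over six weeks, the need is greater over the longer interval that follows.

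Retention is one of three stated questions. As planned, it would be answered with a number that does not address it.

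**Working it through.** **1. Plan's own figure.** The plan gives no numerical basis for the retention analysis, so there is nothing to reproduce. Its only sample-size figure, 16 to 24 children per study (section 1), is not tied to retention. It is used below only to set the number of children.

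**2. Length of the interval.** Six weeks is 6 / 4.35 = 1.38 months. The follow-up wait is therefore 2 / 1.38 = 1.4 to 4 / 1.38 = 2.9 times the treatment period. One child's wait may be 4 / 2 = 2 times another's.

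**3. What tau responds to.** Tau depends only on the ordering of children at the two times. Without measurement noise, it equals 1.0 if every child gains 15 points, if every child loses 30 points, and if every child keeps only 20% of the score.

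**4. The same with noise.** The documents give no score distribution, so these inputs are assumed: end-treatment scores normal with mean 50 and SD 20; follow-up equals end-treatment score plus the stated change plus noise of SD 10; scores unbounded; 3,000 replicates. As a check on the no-change case, the normal-theory value is (2/π) × arcsin(20 / √(20² + 10²)) = (2/π) × arcsin(0.894) = 0.705.

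| Change between end of treatment and follow-up | Mean tau, n = 16 | Mean tau, n = 24 |
|---|---|---|
| None | 0.705 | 0.707 |
| All gain 15 | 0.707 | 0.703 |
| All lose 30 | 0.704 | 0.704 |
| Growth 5 points a month, wait uniform on 2 to 4 months | 0.692 | 0.694 |
| Growth 10 points a month, same wait | 0.665 | 0.666 |
| Random half gain 20 (outside therapy) | 0.605 | 0.602 |
| Random half gain 40 | 0.459 | 0.457 |
| Growth larger in children with higher end-treatment scores | 0.764 | 0.766 |

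The first three rows cannot be told apart, although one is full retention and another is a large loss. In the remaining rows nothing is lost, yet tau falls or rises with the pattern of outside gains.

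**5. Why Target levels alone are not enough.** Write T and C for Target and Control scores, with 0 for pretreatment, 1 for end of treatment and 2 for follow-up. The change T2 − T1 is the change in the treatment effect plus growth over the wait; one number cannot separate the two. Define

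- effect at end of treatment: E1 = (T1 − T0) − (C1 − C0)
- effect at follow-up: E2 = (T2 − T0) − (C2 − C0)
- change in effect: E2 − E1 = (T2 − T1) − (C2 − C1)

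Growth common to both forms cancels from E2 − E1, whatever the child's wait.

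**6. Price in precision.** If the two changes have equal variance and correlation r, the SD of E2 − E1 is √(2(1 − r)) times that of T2 − T1. With r = 0 this is 1.41; the contrast is noisier unless r exceeds 0.5.

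**The case against.** The strongest reply is that the plan does not say Control is omitted at follow-up. The retention sentence names no form, and the generalization probes it refers to are described earlier as covering both. That stands: a reader might infer that only treated forms are probed, but the documents support only that the form is unspecified. The gap in the analysis remains, because no contrast is planned whichever forms are probed.

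A second reply concerns direction. A reader might infer that growth and later therapy would be credited as retained learning in the planned result. They would not, as a rule. Growth shared by all children leaves tau unchanged, and uneven waits or therapy mostly lower it, so retention would tend to look the same or poorer. The exception is growth that tracks end-treatment level. Crediting growth as retention is a fault of a level comparison, which the plan does not contain. For the same reason no percentage of hidden loss can be attached to the plan; the documents give neither a growth rate nor an expected gain.

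Third, effectiveness and the benefit of semantic support both rest on end-of-treatment d and are untouched. That is correct, and it limits the weight of the point.

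Fourth, Target minus Control does not fully remove outside therapy, since a clinician may work on only one of the two forms. This also stands. It is a reason to record interval therapy, not a reason to go without a reference.

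**Conclusion.** The concern holds for the retention question. As written, the analysis cannot show how much of the treatment effect persisted: under the assumed inputs, mean tau is about 0.70 to 0.71 whether every child keeps the score, loses 30 points or gains 15. Insensitivity to a common shift is a property of ranks and does not depend on the assumed mean, SD or noise. It does require that scores are not pushed to a floor or ceiling, where ties would change tau. The sizes for uneven growth and therapy do depend on the assumptions and only illustrate that the distortion can run either way.

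The plan should be changed before follow-up data are analysed. This is more than missing detail: the analysis that is specified does not address the stated question, and one that does is available from the plan's own control logic. No corrected estimate can be computed, because the documents give no follow-up SD, growth rate or dropout.

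**What to change.** - Name the forms probed at follow-up, and probe both Target and Control there.
- Make the main retention estimate the Target-minus-Control change from pretreatment at follow-up, compared within child with the same quantity at end of treatment, on one scale at both times. The plan's Bayesian signed-rank test can be used. Report the size of the change with its interval as well as the Bayes factor.
- Keep Kendall's tau as a secondary description of rank stability, and do not call it the degree of retention.
- Record days since last treatment and parent-reported language therapy in the interval, including which form was worked on if known. Report these descriptively; 16 to 24 children are too few for useful subgroups.

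**Cost.** Two data fields, a few sentences of analysis text and, if Control is not already probed at follow-up, a slightly longer visit. The difference score will usually be noisier than the Target score alone. The contrast assumes that both forms would grow equally without treatment, and it gives only partial protection where outside therapy addresses one form and not the other.

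### Group balance influences which grammatical form is treated and measured, but no random or concealed allocation is described and the form is not said to be fixed before the group is known

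*Combined protocol and SAP*

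**What the plan says.** The statements that bear on this point are spread over three parts of the combined protocol and SAP.

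- **Section 3, Research procedures.** The design is given as "This study will compare two variants of the same treatment": verb meanings are explained in one and not in the other. No method of assigning children to a variant follows. The same section says that "children's language will be sampled periodically to determine which aspects of speech and language are in error and should be treated".
- **Section 3, Treatment methods.** Among the reasons why exact wording cannot be listed in advance, the plan says that "the linguistic units targeted for treatment are tailored to the errors of omission or commission for each individual child enrolled", adding "These are never uniform across all children". The next reason is that "research considerations such as balancing particular targets across treatment groups influence the decision on what to treat, and therefore, the words used".
- **Analysis plan.** A single-subject d is built from pretreatment and end-treatment generalization probes. Of this d the plan says: "This is calculated for each of the Target and Control morphemes as follows". For the semantic-support question, "we will compare the treatment d for children who did and did not receive semantic support during treatment". The between-group method is a Bayesian version of the Mann-Whitney test, with no stratification or covariate for form.

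Section 1 adds that children with too few potential targets are withdrawn after testing.

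**The concern.** In most trials the outcome measure is the same for every child. Here it is not: the form selected for treatment defines the child's Target d. Whoever selects the form therefore also selects the outcome.

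The plan says this selection is influenced by balance across the groups being compared. To balance groups through the choice of form, the chooser needs to know the child's group, or at least how the groups are made up so far. The aim is sound, but the method gives the arm a route into the outcome. If forms differ in how readily they improve, a difference in d between arms could partly reflect which forms were picked rather than whether verb meanings were supplied.

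This matters more because the Analysis plan itself expects only modest evidence from a comparison of two efficacious variants. A small selection effect could be mistaken for a semantic-support effect, or could hide one. An unadjusted rank test offers no protection. Adjusting for type of form would not fully repair a choice made with the arm known.

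**Working it through.** The plan gives no figure on this point, so there is none to reproduce. The check is whether the text leaves a route from arm to outcome form, and whether balancing closes it.

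**Step 1. Is there a choice to be made within a child?** Yes. Targets are tailored to each child's own errors and differ between children. Section 1 withdraws children with too few potential targets, and the analysis needs both a Target and a Control form. Retained children should therefore have more than one candidate form.

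**Step 2. Is the chosen form the one measured?** Yes. The Analysis plan computes d on each child's Target and Control morphemes and compares it between arms.

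**Step 3. Is the choice separated from the arm?** Nothing in the text says so. The possible orders are:

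- *Form first, then random concealed allocation.* The route is closed. The plan does not describe this.
- *Form first, then children placed so as to balance forms.* The form cannot depend on the arm, but assignment is then not shown to be random.
- *Group first, then form.* The form can depend on the arm. This is the most natural reading of a sentence in which balance influences what is treated, but the order is not stated.

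**Step 4. Does balancing close the route?** Only in part. Write the gain that child i would show on form f without semantic support as

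g(i, f) = m(type of f) + e(i, f),

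where m is the average for that type of form and e is how far this child's form lies above or below that average, for example because it is already emerging. The expected arm contrast is then

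semantic-support effect + (difference between arms in mean m) + (difference between arms in mean e).

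An equal mix of form types makes the second term zero. It does nothing to the third, because two arms with identical counts of each type can still differ in which children had that type selected. If forms are fixed first and the group is then assigned at random with concealment, both terms are zero in expectation.

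**Step 5. How large is the third term?** It cannot be calculated. The documents give no list of forms, no expected gain by form, no count of candidate forms per child and no record of who chooses with what knowledge.

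**Conditional note on Target versus Control.** The numerator of d is the end-treatment probe mean minus the pretreatment probe mean. Suppose the lower-scoring of a child's forms became the Target, and that judgement used the same pretreatment probes. The Target baseline would then be low partly by chance, would tend to rise on remeasurement, and would inflate the Target-Control contrast. The documents state neither condition. The same rule applied in both arms would not by itself produce a difference between arms.

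**The case against.** The strongest reply is that balancing is a safeguard. It aims to give both arms a similar mix of forms, which reduces confounding by type of form. That stands, and a reader who inferred that the arms will have different mixes, and put a number on the resulting bias, would be describing a design without the balancing that this plan states. What survives is selection within a child, which balancing of types does not prevent.

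A second reply is that the sentence explains why wording cannot be listed in advance and does not describe allocation. Targets may be settled from testing before any child has a group. This also has force: the order is unstated. But the sentence says balance influences what is treated, not who is placed where. Even if forms did come first, the plan would still lack a described random, concealed assignment.

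Third, silence about randomisation does not prove its absence. Agreed. A reader might infer that the trial is not randomised, but the documents support only that no method is described.

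Fourth, a reader might infer that the choice between Target and Control is unconstrained, or that regression to the mean is built into the Target-Control comparison. The documents do not say how Control forms are chosen, or that the baseline probes are used to choose any form. Neither inference can be asserted.

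**Conclusion.** The point holds as a weakness in the design as written. Group balance influences the choice of the form that defines the outcome, the arms are compared on that outcome without adjustment, and neither random concealed allocation nor prior fixing of the form is described. The semantic-support contrast is therefore open to selection within children.

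The conclusion rests on two assumptions: that forms within a child can differ in their prospects of improving, and that the chooser may know the arm. The text does not exclude the second and makes it plausible. No magnitude can be given, and the documents do not show that selection has taken place. The change should be made because the same balance can be had without this exposure. Confidence is medium, since the order of events is inferred.

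**What to change.** 1. Record each child's Target and Control forms, chosen from that child's errors by the plan's usual tailoring, before the group is known.
2. Then assign the group at random from a concealed list, stratified or minimised on Target form. State the allocation ratio and who holds the list.
3. Replace the sentence under Treatment methods so that balance comes from allocation. Suggested text: *Target and Control forms are selected from each child's errors and documented before group assignment. Comparability of forms across groups is achieved by stratifying or minimising the random assignment on Target form.*
4. State that the measurements used to choose forms are separate from the pretreatment probes that enter d. This also removes the conditional regression-to-the-mean problem.
5. For children already assigned, state the method and order actually used, and tabulate Target forms by arm.

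**Cost.** Protocol wording and a prepared list, with no added children. Staff lose some freedom to match forms to groups. At the 16 to 24 children per study given in section 1, strata will be small, so minimisation on one factor may be needed. If the measurements that choose forms currently double as baseline probes, separating them could add some testing time.

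### The analysis plan describes the Bayes factor as a probability, and 1/BF as the probability that two distributions are equivalent; both are evidence ratios, and a BF below 1 needs a correct reading rule

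*Combined protocol and SAP*

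**What the plan says.** All of this is in the combined protocol and SAP, section 3, under Analysis plan.

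- The paragraph on the Bayesian approach says that Bayesian statistics "express the probability that two distributions are different", and continues: "This probability is expressed as a Bayes Factor (BF), which can range from 0 to infinity".
- It then turns to equivalence: "A Bayesian approach can also evaluate the probability that two distributions are equivalent", with 1/BF given in brackets as the quantity for group differences.
- Two sentences follow on what is expressed. For group differences, "this expresses the range of effect sizes from within which the true effect is likely to fall"; for correlations, "it expresses the range of correlations from which the true correlation is likely to fall". No interval is named in either.
- The next paragraph treats BF as a degree of support that grows above 1.0. Its bands are 1 to 3 weak, "moderate support indicated by BFs between 3 and 10", and above 10 strong. It gives no band below 1. It adds that a comparison of two efficacious treatments "is unlikely to result in a BF large enough to meet this criterion" for strong support.
- The final paragraph sets the comparison affected: "To address whether providing semantic support improves learning, we will compare the treatment d" between children with and without semantic support.

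The plan gives no prior odds, no equivalence margin and no calculation of a posterior probability.

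**The concern.** A quantity with no upper limit cannot be a probability, and the reciprocal of an evidence ratio is not one either. The plan therefore gives its readers a wrong rule for the main statistic.

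The rule matters most for a BF below 1. Above 1, the bands provide a sound reading as strength of support. Below 1, nothing is provided except the sentence that equates 1/BF with a probability of equivalence. If the semantic-support comparison returns a BF below 1, an author who follows the plan would report it as the probability that the two variants are equivalent. The result would in fact be relative, and perhaps weak, evidence for an exactly zero difference, and could still be compatible with a sizeable effect in either direction.

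**Working it through.** **1. The definition (no assumptions needed).** BF10 = p(data | difference) / p(data | no difference), and 1/BF10 is the inverse ratio. For BF of 0.8, 0.5 and 0.2, 1/BF is 1.25, 2 and 5. All exceed 1, so the reading as a probability fails whenever BF is below 1. It also fails above 1: BF = 3 gives 1/BF = 0.333, but at equal prior odds the probability of no difference is 1/(1 + 3) = 0.25.

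**2. What turns 1/BF into a probability.** P(no difference | data) = (1/BF × prior odds) / (1 + 1/BF × prior odds), where the prior odds are those of no difference against a difference. The plan gives no prior odds, so I use three values. With 1/BF = 2.34 (from step 3):

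| Prior P(no difference) | Prior odds | Calculation | Posterior |
|---|---|---|---|
| 0.2 | 0.25 | 0.585 / 1.585 | 0.37 |
| 0.5 | 1 | 2.34 / 3.34 | 0.70 |
| 0.8 | 4 | 9.36 / 10.36 | 0.90 |

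With 1/BF = 2.68 the same steps give 0.67/1.67 = 0.40, 2.68/3.68 = 0.73 and 10.72/11.72 = 0.91. A single BF fixes no single probability. Any probability so obtained concerns a difference of exactly zero, not one within a margin.

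**3. Illustration of what a BF below 1 could mean here.** The only input from the plan is 16 to 24 children per study (section 1, Study Population). My assumptions are that this is the total, that the arms are equal (16/2 = 8, 24/2 = 12), that the test is two-sided, that the prior on the standardised arm difference δ is Cauchy with scale 0.707, and that a Bayesian t-test can stand in for the planned rank test. Here δ is in units of the between-child SD of the per-child d.

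BF10 = ∫ f(t | δ) π(δ) dδ / f(t | 0), where f is the noncentral t density with n1 + n2 − 2 degrees of freedom and noncentrality δ√(n1n2/(n1 + n2)), and π is the Cauchy prior. The credible interval comes from the posterior proportional to f(t | δ) π(δ). The two-sided BF is smallest at an observed difference of zero (t = 0):

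| Per arm | Smallest BF | Largest 1/BF | 95% credible interval for δ |
|---|---|---|---|
| 8 | 0.428 | 2.34 | ±0.80 |
| 12 | 0.373 | 2.68 | ±0.68 |

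A latent-normal rank sampler, run for the zero-difference case with balanced ranks, gave 1/BF of 2.31 and 2.66 with intervals of ±0.81 and ±0.68, so the stand-in is adequate at that point. Ordinary 95% confidence intervals, which are not shrunk by the prior, are wider: ±1.07 and ±0.85.

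**4. Sensitivity.** If 16 to 24 is per arm, the largest 1/BF is 2.97 to 3.48, which crosses the plan's line for moderate support. With 8 to 12 per arm and a prior scale of 0.5 it is 1.91 to 2.14; with scale 1.0 it is 2.97 to 3.48. A one-sided test has no ceiling at zero: 1/BF keeps rising as the observed difference goes against semantic support, and is 5.34 (8 per arm) and 6.52 (12 per arm) at t = −2.

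**The case against.** **No equivalence question is planned.** The final paragraph of the Analysis plan asks whether treated forms gain more than control forms, whether semantic support helps, and whether learning is retained. The sentence on equivalence is general background. This stands. A reader might infer that the trial means to claim that the variants are equivalent, or that it expects a BF below 1. The documents say neither; they say only that a strong BF is unlikely.

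**The misreading limits itself.** A value such as 2.34 cannot be printed as a probability. That is true of the number. It does not prevent a verbal report that the variants are probably equivalent, and the plan offers no other wording for such a result.

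**The next paragraph already reads BF correctly, as support for a hypothesis.** It does, and the tests, software and comparisons are unaffected. But its bands start at 1 and are not said to apply to 1/BF, so the repair is partial.

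**The sentences on ranges.** A reader might take them as a further definition of BF, as a range of effect sizes or correlations. The natural reading is a credible interval whose name is missing. That is an editing gap, and I treat it as one.

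**The illustration rests on assumptions.** It does. The plan states neither the prior scale nor the direction of the test. That is a separate missing-detail point and does not follow from the error in definition. It also means that a reader should not conclude that moderate support for no difference is out of reach: under other readings of the sample size, prior or direction it is attainable.

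**Conclusion.** The concern holds as an error of definition and interpretation. Calling BF a probability of a difference, and 1/BF a probability of equivalence, is wrong without any assumption. The consequence is confined to how a BF below 1 in the semantic-support comparison would be read and reported; the planned tests remain valid.

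The figures show scale only. Under the stated assumptions, even the two-sided result most favourable to no difference would fall in the plan's weak band if the bands were applied to 1/BF, and its interval would still include effects of about 0.7 to 0.8 SD in both directions. That does not show equivalence. Confidence in the definitional point is high; the numerical ceiling depends on the sample size reading, prior and direction.

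**What to change.** In the Analysis plan:

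1. Define BF10 as the evidence ratio for a difference over no difference, and delete the statements that BF or 1/BF is a probability.
2. Say that the weak, moderate and strong bands also apply to 1/BF, as support for no difference and not as equivalence.
3. Name the 95% credible interval in the two sentences on ranges of effect sizes and correlations, and report it for the difference between arms.
4. Make no equivalence claim unless a margin is fixed before analysis. If no such claim is intended, no margin is needed.

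The cost is wording and reporting only. No new data and no change of test are needed, and the interval comes from the same posterior. The consequence to accept is that a BF below 1 can then be reported only as relative, possibly weak, support for no difference.
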